#### **8.3.4.1 Severity of Adverse Events**

All AEs or SAEs will be assessed for severity, according to the toxicity grading scales in the FDA “Toxicity Grading Scale for Healthy Adult and Adolescent Volunteers Enrolled in Preventive Vaccine Clinical Trials”.

For AEs not included in the protocol-defined grading system, the following guidelines will be used to describe severity.

- Mild (Grade 1): Events that are usually transient and may require only minimal or no treatment or therapeutic intervention and generally do not interfere with the subject’s usual activities of daily living.
- Moderate (Grade 2): Events that are usually alleviated with additional specific therapeutic intervention. The event interferes with usual activities of daily living, causing discomfort but poses no significant or permanent risk of harm to the research subject.
- Severe (Grade 3): Events interrupt usual activities of daily living, or significantly affects clinical status, or may require intensive therapeutic intervention. Severe events are usually incapacitating.

AEs characterized as intermittent require documentation of onset and duration of each episode. The start and stop date of each reported AE will be recorded on the appropriate DCF. Changes in the severity of an AE will be documented to allow an assessment of the duration of the event at each level of intensity.

#### **8.3.4.2 Relationship to Study Intervention**

For each reported adverse reaction, the participating site PI or qualified designee must assess the relationship of the event to the study product using the following guidelines:

- Related – The AE is known to occur with the study intervention, there is a reasonable possibility that the study intervention caused the AE, or there is a temporal relationship between the study intervention and event. Reasonable possibility means that there is evidence to suggest a causal relationship between the study intervention and the AE.
- Not Related – There is not a reasonable possibility that the administration of the study intervention caused the event, there is no temporal relationship between the study intervention and event onset, or an alternate etiology has been established.

#### **8.3.5 Time Period and Frequency for Event Assessment and Follow-Up**

For this study:

- solicited AEs will be collected from Days 1-8 (7 days post first vaccination) and Days 29-36 (7 days post second vaccination).
- unsolicited AEs will be collected from Days 1-57.

- SAEs, Protocol Specified AESIs, MAAEs, and NOCMCs will be collected from Day 1 through the end of the study (Day 394).

### **8.3.6 Adverse Event Reporting**

#### **8.3.6.1 Investigators Reporting of AEs**

Information on all AEs should be recorded on the appropriate DCF. All clearly related signs, symptoms and results of diagnostic procedures performed because of an AE should be grouped together and recorded as a single diagnosis. If the AE is a clinical laboratory abnormality that is part of a clinical condition or syndrome, it should be recorded as the syndrome or diagnosis rather than the individual clinical laboratory abnormality. Each AE will also be described in terms of duration (start and stop date), severity, association with the study product, action(s) taken, and outcome.

### **8.3.7 Serious Adverse Event Reporting**

#### **8.3.7.1 Investigators Reporting of SAEs**

Any AE that meets a protocol-defined criterion as an SAE must be submitted immediately (within 24 hours of site awareness) on an SAE form to the DMID Pharmacovigilance Group, at the following address:

DMID Pharmacovigilance Group  
Clinical Research Operations and Management Support (CROMS)  
[name]  
[name]  
SAE Hot Line: [name] (US) or [name] (outside US)  
SAE [contact] (US) or [name] (outside US)  
SAE Email Address: [contact]

In addition to the SAE form, select SAE data fields must also be entered into the SDCC system. Refer to the protocol-specific MOP for details regarding this procedure.

Other supporting documentation of the event may be requested by the DMID Pharmacovigilance Group and should be provided as soon as possible. The DMID Medical Monitor will review and assess the SAE for regulatory reporting and potential impact on study subject safety and protocol conduct.

At any time after completion of the study, if the participating site PI or appropriate sub-investigator becomes aware of an SAE that is suspected to be related to study product, the participating site PI or appropriate sub-investigator will report the event to the DMID Pharmacovigilance Group.

#### **8.3.7.2 Regulatory Reporting of SAEs**

Following notification from the participating site PI or appropriate sub-investigator, DMID, as the IND sponsor, will report any SUSAR in an IND safety report to the FDA and will notify all participating site PIs (i.e., all PIs to whom the sponsor is providing drug under its IND(s) or under any PI's IND(s)) of potential serious risks from clinical studies or any other source, as soon as possible. DMID will report to the FDA any unexpected fatal or life-threatening suspected adverse reaction as soon as possible, but in no case later than 7 calendar days after the

sponsor's initial receipt of the information. If the event is not fatal or life-threatening, the IND safety report will be submitted within 15 calendar days after the sponsor determines that the information qualifies for reporting as specified in 21 CFR Part 312.32. Relevant follow-up information to an IND safety report will be submitted as soon as the information is available. Upon request from FDA, DMID will submit to the FDA any additional data or information that the agency deems necessary, as soon as possible, but in no case later than 15 calendar days after receiving the request.

SAEs that are not SUSARs will be reported to the FDA at least annually in a summary format which includes all SAEs.

### **8.3.8 Reporting Events to Subjects**

Subjects will be informed of any AEs or SAEs that occur as part of their participation in this trial.

### **8.3.9 Adverse Events of Special Interest (AESIs)**

Adverse Events of Special Interest (AESIs) represent any events for which additional data (besides the standard AE data) are desired. These may be at the request of the regulatory agency, industry partner or DMID, and driven by a regulatory requirement, or known or potential risk from the product or class. Non-structured data similar to SAEs will be collected for AESIs. AESIs encompass the following terms:

- Protocol Specified AESIs:
  - All suspected cases of myocarditis or pericarditis should be recorded. For reporting purposes, a subject who displays signs/symptoms consistent with myocarditis or pericarditis should be reported as a potential case of myocarditis or pericarditis.
- NOCMCs – defined as any new ICD diagnosis (per current International Statistical Classification of Diseases and Related Health Problems) that is applied to the subject during the course of the study, after receipt of the study agent, that is expected to continue for at least 3 months and requires continued health care intervention.
- MAAEs – defined as hospitalization, an emergency room visit or an otherwise unscheduled visit to or from medical personnel for any reason.

All AESIs are assessed, recorded, and followed as described above under AEs. AESIs that meet SAE criteria will be reported on an SAE form within 24 hours to the DMID Pharmacovigilance Group, at the following address:

DMID Pharmacovigilance Group  
Clinical Research Operations and Management Support (CROMS)  
[name]  
[name]  
SAE Hot Line: [name] (US) or [name] (outside US)  
SAE [contact] (US) or [name] (outside US)  
SAE Email Address: [[contact]](mailto:[contact])

In addition, for documentation and medical assessment purposes AESIs that do not meet SAE criteria will also be reported on an SAE form within the period for AE reporting to the DMID Pharmacovigilance Group; however, the narrative will indicate that the AESI did not meet SAE criteria.

### **8.3.10 Reporting of Pregnancy**

Pregnancy is not an AE. However, any pregnancy that occurs during study participation (through Day 394) should be reported to the sponsor on the appropriate DCF. Pregnancy should be followed to outcome.

## **8.4 Unanticipated Problems**

### **8.4.1 Definition of Unanticipated Problems (UPs)**

The Department of Health and Human Services (DHHS) OHRP considers unanticipated problems involving risks to subjects or others to include, in general, any incident, experience, or outcome that meets all of the following criteria:

- Unexpected in terms of nature, severity, or frequency given (a) the research procedures that are described in the protocol-related documents, such as the IRB-approved research protocol and informed consent document; and (b) the characteristics of the subject population being studied;
- Related or possibly related to participation in the research (“possibly related” means there is a reasonable possibility that the incident, experience, or outcome may have been caused by the procedures involved in the research); and
- Suggests that the research places subjects or others at a greater risk of harm (including physical, psychological, economic, or social harm) than was previously known or recognized.

### **8.4.2 Unanticipated Problem Reporting**

To satisfy the requirement for prompt reporting, UPs will be reported using the following timeline:

- UPs that are SAEs will be reported to the IRB and to the SDCC/study sponsor within 24 hours of the participating site PI or appropriate sub-investigator becoming aware of the event per the above described SAE reporting process.
- UPs that are SAEs will be collected from Day 1 through the end of the study (Day 394).
- Any other UP will be reported to the IRB and to the SDCC/study sponsor within 3 days of the participating site PI or appropriate sub-investigator becoming aware of the problem.
- UPs that are not SAEs will be collected from Days 1-57.

### **8.4.3 Reporting Unanticipated Problems to Subjects**

Subjects will be informed of any UPs that occur as part of their participation in this trial.

## 9. STATISTICAL CONSIDERATIONS

### 9.1 Statistical Hypotheses

This is a phase I, open-label, dose-ranging clinical trial and is not designed to test a specific hypothesis. Rather, it is intended to obtain preliminary estimates in healthy adults of the safety, reactogenicity, and immunogenicity of mRNA-1273.

### 9.2 Sample Size Determination

Rare AEs are not demonstrable in a clinical study of this size; however, the probabilities of observing one or more AEs given various true event rates are presented in [Table 9](#). With the assumption that all enrolled subjects will likely complete immunizations and safety visits in this relatively short duration study, the following statistical considerations apply. With 15 subjects in each dose group (cohorts 1-3,10,13), the chance of observing at least one AE of probability 20% or more is approximately 97%. Therefore, if no AEs of a given type occur in a dose group (cohorts 1-3,10,13), we can be relatively confident that they will occur in fewer than 20% of people once the vaccine is implemented. With 60 subjects across these four dosing cohorts (1-3,10), the chance of observing at least one AE of probability 5% or more is at least 95%. Therefore, if no AEs of a given type occur across the combined doses, we can be very confident that any dosage-independent event will occur in fewer than 5% of people once the vaccine is implemented. If Cohort 13 is enrolled and there are 75 subjects across five dosing cohorts (1-3,10,13), the chance of observing at least one AE of probability 5% or more is at least 97.9%. Therefore, if no AEs of a given type occur across the combined doses, we can be very confident that any dosage-independent event will occur in fewer than 5% of people once the vaccine is implemented. With 10 subjects in each dose group (cohorts 4-9,11-12), the chance of observing at least one AE of probability 20% or more is approximately 89.3%. Therefore, if no AEs of a given type occur in a dose group (cohorts 4-9,11-12), we can be relatively confident that they will occur in fewer than 20% of people once the vaccine is implemented in the older population. With 30 subjects across each of the two older subject dosing cohorts (i.e., cohorts 4,5,11 and 7,8,12), the chance of observing at least one AE of probability 5% or more is at least 78.5%. Therefore, if no AEs of a given type occur across the combined doses, we can be very confident that any dosage-independent event will occur in fewer than 5% of older people once the vaccine is implemented. If Cohorts 6 and 9 are enrolled and there are 40 subjects across each of the two older subject dosing cohorts (i.e., cohorts 4,5,6,11 and 7,8,9,12), the chance of observing at least one AE of probability 5% or more is at least 87.1%. Therefore, if no AEs of a given type occur across the combined doses, we can be very confident that any dosage-independent event will occur in fewer than 5% of older people once the vaccine is implemented.

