- b) Clinical screening laboratory evaluations will include WBCs, Hgb, PLTs, Cr, ALT, AST, ALP, T. Bili, Lipase, PT, PTT, hepatitis B surface antigen, hepatitis C virus antibody, and HIV types 1 and 2 antigen/antibody. Clinical safety laboratory evaluations obtained on Days 1, 8, 29, and 36 will include WBCs, Hgb, PLTs, Cr, ALT, AST, ALP, T. Bili, and Lipase.
- c) For women of childbearing potential serum pregnancy test at screening, and urine or serum pregnancy test on Days 1 and 29 with results confirmed as negative prior to enrollment on Day 1 and administration of each vaccination.
- d) Depending on the timepoint approximately 8 or 16 mL of each venous blood sample is designated for secondary research.
- e) For those subjects consented for leukapheresis, screening procedures, including screening laboratory evaluations, will be performed locally prior to the leukapheresis procedure. Refer to the protocol-specific MOP for details on the leukapheresis procedure.
- f) Visits 09-14 windows should be based off the actual Visit 06 date.
- g) Subjects who participate in the optional third mRNA-1273 vaccination substudy will exit the Schedule of Activities for the main study between Visit 13 and the close of the window for Visit 14 and will not have Visit 14, instead will have Visit 14A and subsequent substudy visits. See [Section 12](#), Appendix A for the Schedule of Activities for the optional third mRNA-1273 vaccination substudy.

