## 3. OBJECTIVES AND ENDPOINTS

**Table 5: Objectives and Endpoints (Outcome Measures)**

OBJECTIVES	ENDPOINTS (OUTCOME MEASURES)
Primary	

 
To evaluate the safety and reactogenicity of a 2-dose vaccination schedule of mRNA-1273, given 28 days apart, across 5 dosages in healthy adults.
 
	
 
Frequency and grade of each solicited local and systemic reactogenicity AE during a 7-day follow-up period post each vaccination.
 
Frequency and grade of any unsolicited AEs during the 28-day follow-up period post each vaccination.
 
Frequency of any SAEs, Protocol Specified AESIs, NOCMCs, and MAAEs from Day 1 to Day 394.
 

Secondary	

 
To evaluate the immunogenicity as measured by IgG ELISA to the SARS-CoV-2 S (spike) protein following a 2-dose vaccination schedule of mRNA-1273 at Day 57.
 
	
 
GMT of antibody at Day 57.
 
Percentage of subjects who seroconverted, defined as a 4-fold change in antibody titer from baseline.
 
The GMFR in IgG titer from baseline.
 

Exploratory	

OBJECTIVES	ENDPOINTS (OUTCOME MEASURES)

 
To evaluate the immunogenicity as measured by IgG ELISA to the SARS-CoV-2 S (spike) protein following a 2-dose vaccination schedule of mRNA-1273 at all timepoints, other than Day 57.
 
	
 
GMT of antibody at each timepoint.
 
Percentage of subjects who seroconverted at each timepoint.
 
The GMFR in IgG titer from baseline at each post-vaccination timepoint.
 

 
To evaluate the immunogenicity as measured by IgM and IgA ELISA to the SARS-CoV-2 S (spike) protein following a 2-dose vaccination schedule of mRNA-1273 given 28 days apart.
 
	
 
GMT at each timepoint.
 
Percentage of subjects who seroconverted at each timepoint.
 
The GMFR in IgM and IgA titer from baseline at each post-vaccination timepoint.
 

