### 9.3 Populations for Analyses

The Safety Analysis population for the main study includes all subjects who received one dose of vaccine. Analyses for the primary safety population will include safety reported through the end of the main study. A modified primary safety population analysis will also be performed that excludes safety data collected after subjects receive either the third mRNA-1273 vaccination in the optional substudy or non-study EUA vaccine, if applicable.

The modified intent-to-treat (mITT) population includes all subjects who received one dose of vaccine and contributed both pre- and at least one post-vaccination venous blood samples for immunogenicity testing for which valid results were reported.

In the final analysis, protocol deviations will be reviewed to determine which protocol deviations may affect the analysis. The per protocol (PP) population will then be defined – and this includes all subjects in the mITT subset with the following exclusions:

- Data from all available visits for subjects found to be ineligible at baseline.
- Data from all visits subsequent for the protocol deviations that are considered to affect the science.

- Data from any visit that occurs substantially out of window.

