**Table 13: Treatment Arms and Substudy Dosing**

Cohort	Sample Size**	Stratum (Years of Age)	First and Second Dose in Main Study	Optional Third Dose in Substudy
1	15	18-55	25 mcg mRNA-1273	100 mcg mRNA-1273
2	15	18-55	100 mcg mRNA-1273	100 mcg mRNA-1273
3	15	18-55	250 mcg mRNA-1273	100 mcg mRNA-1273
4	10	56-70	25 mcg mRNA-1273	100 mcg mRNA-1273
5	10	56-70	100 mcg mRNA-1273	100 mcg mRNA-1273
6*	10	56-70	250 mcg mRNA-1273	n/a
7	10	≥71	25 mcg mRNA-1273	100 mcg mRNA-1273
8	10	≥71	100 mcg mRNA-1273	100 mcg mRNA-1273
9*	10	≥71	250 mcg mRNA-1273	n/a
10	15	18-55	50 mcg mRNA-1273	100 mcg mRNA-1273
11	10	56-70	50 mcg mRNA-1273	100 mcg mRNA-1273
12	10	≥71	50 mcg mRNA-1273	100 mcg mRNA-1273
13*	15	18-55	10 mcg mRNA-1273	n/a

\*Cohorts 6, 9 and 13 were not enrolled.

\*\*\*Four subjects did not receive the second dose of mRNA-1273 in the main study. Three subjects discontinued due to an AE (hives on lower extremities judged related to the first mRNA-1273 vaccination [cohort 1], sore throat [cohort 3], and maculopapular rash [cohort 5]); the other subject discontinued treatment due to quarantine for a COVID-19 exposure (cohort 1).

The third mRNA-1273 vaccination will be offered to subjects who received 2 doses of 25 or 50 mcg (cohorts 1, 4, 7, 10, 11, and 12), which are lower than the EUA mRNA-1273 dosage of 100

mcg, as soon as feasible after their Main Study Day 209 visit, and also will be offered to subjects who received 2 doses of 100 and 250 mcg (cohorts 2, 3, 5, and 8) no later than the close of the window for their originally scheduled Main Study Day 394 visit.

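### The detection probabilities in Protocol 9.2 and SAP 5 assume complete follow-up and do not hold for Day 1-394 events in the modified (two-dose-only) safety analysis

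*Protocol*

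**What the plan says.** Protocol 9.2 opens its probabilities with a completion assumption: "With the assumption that all enrolled subjects will likely complete immunizations and safety visits in this relatively short duration study". SAP 5 repeats it. For 15 subjects the text then says "the chance of observing at least one AE of probability 20% or more is approximately 97" percent, and for the 60 subjects aged 18-55 "the chance of observing at least one AE of probability 5% or more is at least 95" percent. For the older cohorts it gives 89.3% (N=10, 20% event) and 78.5% (N=30, 5% event). Each figure is followed by a statement that a zero count supports a true rate below 20% or 5%.

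One primary endpoint group runs long (Table 5): "Frequency of any SAEs, Protocol Specified AESIs, NOCMCs, and MAAEs from Day 1 to Day 394". The other two cover 7 and 28 days after each dose, so they end by Day 57.

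Under Table 4, footnote g, third-dose recipients "will exit the Schedule of Activities for the main study between Visit 13 and the close of the window for Visit 14" and have no Visit 14. Section 12.5 (text below Table 13) offers the dose to the 25 and 50 mcg cohorts "as soon as feasible after their Main Study Day 209 visit", and to the 100 and 250 mcg cohorts by the close of the Day 394 window at the latest.

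Protocol 9.3 keeps a primary safety analysis running to the end of the main study and adds another: "A modified primary safety population analysis will also be performed that excludes safety data collected after subjects receive either the third mRNA-1273 vaccination" or a non-study vaccine under emergency authorization. The SAP has neither this modified analysis (see SAP 6.2.3) nor a rule for third-dose data. SAP 9.3 sets the incidence denominator at the total population size, and SAP Table 138 lays out SAEs, MAAEs and NOCMCs as n and % by dose column.

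**The concern.** The amendment history shows Protocol 9.3 revised for the substudy in version 6.0 (January 2021). The last listed change to 9.2 is in version 4.0 (May 2020). For the substudy itself, Protocol 12.11.2 does recompute detection for partial uptake (5 subjects in a cohort, 67%). The main study has no counterpart.

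In the modified analysis, a 25 or 50 mcg subject who takes the third dose contributes two-dose data only to a day somewhere between 209 and 394, yet 9.2 counts that subject in full. Two things are at stake. A zero count of a late event in one of these cohorts would be read with more assurance than it carries. And because the offer comes earlier at the lower doses, percentages over the full population could make those doses look safer through shorter observation alone.

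**Working it through.** **1. The plan's own figures.** With P = 1 - (1 - p)^N:

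- N=15, p=0.20: 1 - 0.80^15 = 96.5%
- N=10, p=0.20: 1 - 0.80^10 = 89.3%
- N=60, p=0.05: 1 - 0.95^60 = 95.4%
- N=30, p=0.05: 1 - 0.95^30 = 78.5%

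All 60 entries of Protocol Table 9 reproduce within 0.1 point.

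**2. Who can exit early.** The 25/50 mcg cohorts (1, 4, 7, 10, 11, 12) have 15 + 10 + 10 + 15 + 10 + 10 = 70 planned subjects. The note to Table 13 says two cohort 1 subjects had no second dose, and 12.6.1 makes them ineligible. That leaves 68. In the 18-55 group of 60, 15 + 13 = 28 can exit and 32 are treated as staying. In each older group of 30, 20 can exit and 10 are treated as staying.

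**3. Assumptions (not in the documents).** Constant hazard over Day 1-394 (393 days), uptake from 0 to 100% in the 25/50 mcg cohorts, and full follow-up at 100/250 mcg. Two exit days are used:

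- Day 209, the earliest the rule allows: f = 208/393 = 0.529.
- About Day 271. The substudy entered in version 6.0, dated January 28, 2021. Section 4.1 refers to interim immunogenicity data available on May 15, 2020, and the first post-dose draw is Day 15 ± 2. If those data included such a draw, the earliest-dosed subjects were at Day 13 or later on May 15. The interval to January 28 is 258 days, and 13 + 258 = 271. So f = 270/393 = 0.687.

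**4. Formula.** P = 1 - (1 - p)^(n_stay + n_exit × f). Exponents at full uptake, exit at Day 209 then Day 271:

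- Cohort 10: 15f = 7.94; 10.31
- Cohort 1: 2 + 13f = 8.88; 10.93
- N=10 (cohorts 4, 7, 11, 12): 10f = 5.29; 6.87
- N=60: 32 + 28f = 46.8; 51.2
- N=30: 10 + 20f = 20.6; 23.7

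**5. Detection in two-dose-only data.**

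| Group, event rate | No uptake | 50% uptake, Day 209 | Full uptake, Day 209 | Full uptake, Day 271 |
|---|---|---|---|---|
| Cohort 10, 20% | 96.5% | 92.3% | 83.0% | 90.0% |
| Cohort 1 (13 eligible), 20% | 96.5% | 93.0% | 86.2% | 91.3% |
| N=10, 20% | 89.3% | 81.8% | 69.3% | 78.4% |
| N=60, 5% | 95.4% | 93.5% | 90.9% | 92.8% |
| N=30, 5% | 78.5% | 72.7% | 65.2% | 70.4% |

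**6. Unequal follow-up by dose.** A true 20% event at every dose would show, in a 25/50 mcg cohort that exits entirely, as 1 - 0.8^0.529 = 11.1% (Day 209) or 1 - 0.8^0.687 = 14.2% (Day 271), against 20% in a cohort followed to Day 394.

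**The case against.** The strongest reply is that the primary safety analysis is not cut short. Protocol 12.5 and 12.11.8 collect SAEs, AESIs, MAAEs and NOCMCs through 12 months after the third dose. Only the additional modified analysis excludes later data. This stands. A reader might infer that the lower-dose cohorts were watched for only about half as long, or that detection falls in the primary analysis. The documents do not support either. What the primary analysis does is mix two-dose and three-dose exposure. Listings with vaccination dates, and the doses-received column in SAP Table 257, would let those events be separated.

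Other parts of the reply also stand:

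- Participation is optional and decliners stay to Day 394, so full uptake is a bound and not a forecast.
- Exit comes after Day 209. For the earliest-dosed subjects the dates point to about Day 271 or later. No enrolment dates are given for the other subjects.
- Table 9 is a correct binomial with no stated time window. Reading it as a calculation error would be wrong.
- The 100/250 mcg cohorts may also exit before Day 394. That would narrow the dose imbalance while lowering the pooled figures further.
- Constant hazard is a poor description of some events. Section 2.2.1 places most myocarditis and pericarditis cases, the only Protocol Specified AESIs, within about a week of vaccination, so their detection loses little.
- The trial is descriptive and tests no hypothesis.

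None of this makes the completion assumption true for the modified analysis, or supplies the SAP with a denominator that reflects exposure.

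**Conclusion.** The point holds for one analysis and one endpoint group: SAEs, AESIs, NOCMCs and MAAEs through Day 394 in the modified, two-dose-only analysis of Protocol 9.3. There the full-N probabilities and zero-event statements overstate detection, and by-dose percentages rest on follow-up that depends on dose.

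The size is conditional. Exit at Day 209 can take cohort 10 from 96.5% to as low as 83.0%, a 25/50 mcg cohort of 10 from 89.3% to 69.3%, and a pooled older group from 78.5% to 65.2%. Exit near Day 271 roughly halves the loss for cohort 10 and for the cohorts of 10. All of this assumes constant hazard, full follow-up at 100/250 mcg and full uptake; at zero uptake there is no loss. The contrast of 11.1% with 20% is likewise an extreme case, not an expected result. Events through Day 57 are untouched. This is a defect in how the figures are labelled and how the modified analysis is specified, and does not call the design into question.

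**What to change.** In Protocol 9.2 and SAP 5, state that the full-N probabilities and zero-event statements apply to events through Day 57, and through Day 209 for subjects without a non-study vaccine. Give the Day 1-394 two-dose-only figures as a range over uptake and exit day, with the assumptions stated.

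Carry the modified safety analysis into the SAP. Within it, compare doses for SAEs, AESIs, MAAEs and NOCMCs over the common Day 1-209 window. Report Day 394 results per person-time, censored at a third dose or a non-study vaccine.

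The cost is some rewording, one extra table per age group from dates already collected, and less favourable stated figures for the long-term endpoint. No subjects or visits are added.
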